### **10.3.2 Analysis of Efficacy**

For the primary analysis, the proportion of patients with clinical worsening, defined as a 4.0% decrease from Baseline in resting SpO2 on two successive measurements during home follow-up or hospitalization, will be compared between NasoVAX and placebo groups using the Cochran-Mantel-Haenszel test, while considering the stratification of age groups and risk factors, at a one-sided significance level of 0.025. The same approach will be applied for secondary endpoints that are categorical in nature. Sensitivity analyses will be performed to assess the effect of site on the response to study drug. Linear and logistic regression will be employed to examine the effects of Baseline factors, such as age, sex, medications, and medical co-morbidities on response.

Changes from Baseline in Severity of COVID-19, assessed by average decrease in resting SpO2, average increase in resting pulse rate by outpatient pulse oximetry and COVID-19 symptoms (eDiary) during home follow-up, will be analyzed using a mixed model for repeated measures. The model will include the fixed effects of treatment, week, and treatment-by-visit interaction as well as the continuous, covariate of Baseline level. The model will employ an unstructured within patient covariance matrix and a restricted maximum likelihood estimation method.

A Kaplan-Meier method will be applied to compare changes between treatment groups in resting SpO2 over time.

For the purpose of study efficacy endpoints, resting SpO2 and resting pulse rate will be assessed on observed data only; if data is missing, it will not be imputed.

No multiplicity adjustments will be made for secondary endpoints.

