Upon signing informed consent, patients will undergo Screening assessments at the study center, as per the Schedule of Events ([Table 2](#)). Within each cohort, patients who are determined to be eligible will be randomized that same day (Day 1) in a 1:1 ratio to receive either NasoVAX or placebo with approximately 10 and 14 patients in Cohorts 1 and 2, respectively, receiving NasoVAX and 10 and 14 receiving placebo in Cohorts 1 and 2, respectively ([Table 1](#)). Approximately 24 patients will receive NasoVAX and 24 will receive placebo in Cohort 3. Randomization in Cohort 2 will be stratified by age groups of 35-64 years and 65 years and above. Randomization in Cohort 3 will be stratified by age groups (ages 35-64 years, ages 65 and above) and co-morbidity (one or more risk factors present, no risk factors present). Enrollment of patients ages 35-49 will not exceed approximately 30% of the randomized population of either treatment arm.

Table 1 Study Design

Cohort	Cohort Description	Number of Doses	NasoVAX Dose (vp)	Number of patients	
				NasoVAX	Placebo
1	Ages 35-49 years and risk factors disallowed	Single	1 x 10 ¹¹	10	10
2	Ages 35 and above and risk factors disallowed	Single	1 x 10 ¹¹	14	14
3	Ages 35 and above and risk factors allowed	Single	1 x 10 ¹¹	24	24
Group Total				48	48
Study Total				96	

Study drug will be administered as a single intranasal dose of 0.5 mL (0.25 mL each nostril) in the supine position after which patients must remain in the supine position for 30 minutes. Patients will be observed for at least 2 hours post intranasal administration. Patients who are randomized will be considered enrolled in the study.

No in-person visits are expected during the study after Day 1 unless a participant experiences a change in symptoms or AE that requires a visit for assessment.

Prior to discharge from the study center on Day 1, patients will be provided with:

- A fingertip pulse oximetry device that connects to a mobile device connecting to a tablet that will be supplied to the patient to measure resting SpO₂ and resting pulse rate remotely. Patients will be trained on the use of the device and tablet.
- A digital thermometer for measurement of oral temperature
- Instructions regarding how to take the above measurements and access and complete a web-based electronic diary (eDiary)

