4.2 Schedule of Events

The schedule for study activities is presented in [Table 2](#).

Confidential

Table 2 Schedule of Events – Screening and Treatment Periods

Procedure	Study Visit Type / Day			
	Screening	Study Drug Treatment	Diary Completion/ Telephone Contact	Telephone Contact
	Study Center Visit		Remote Visit	
	Day 1 Pre-Dose	Day 1	Daily Days 1 to 14	Days 21 and 28 ±2 days
Informed consent	X			
Eligibility criteria check	X			
Demographics	X			
Medical history	X			
Focused cardiovascular and respiratory physical examination	X			
Height and weight	X			
Blood pressure and respiratory rate	X			
Urine pregnancy test ^a	X			
Randomization	X			
Study drug administration ^b		X		
Resting SpO ₂ ^c	X		X ^d	
Resting pulse rate ^c	X		X ^d	
Oral temperature ^c	X		X ^d	
Baseline/Concomitant medications	X		X	X
AEs			X	X
eDiary completion for COVID-19 symptoms ^e	X		X	
Criteria for the Assessment of Severity of Illness in Patients with COVID-19 ^f	X			X
Daily telephone contact to document concomitant medications, clinical and hospitalization status and AEs ^g			X	
Follow-up contact for hospitalization status, COVID-19 outcomes, and AEs ^h				X

^a For women of child-bearing potential only. Results must be available and confirmed to be negative before study drug administration.

^b Study drug is to be administered with the patient in the supine position. The patient is to remain in the supine position for 30 minutes thereafter and be observed for at least 2 hours post intranasal administration.

^c To be measured remotely daily at 09:00 and 16:00 hours or at any time the patient experiences worsening symptoms using the study-supplied devices and recorded in the eDiary. Resting SpO₂ and pulse are to be measured at rest for 2 minutes. A ±1 hour window will be allowed. On Day 1, only the afternoon (16:00 hours) measurement is required and may be measured at the study center or remotely.

^d If the Screening visit occurs in the morning, the patient will be responsible for recording the 16:00 measurements at home later that day; if the visit occurs after 16:00, measurements will commence at home the following morning.

Confidential

- ^e The following symptoms will be recorded: fatigue, chills, headache, cough (with or without sputum production), myalgia, sore throat, shortness of breath, nasal congestion, diarrhea, and nausea or vomiting.

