6.2 Efficacy Assessments

6.2.1 *Pulse Oximetry, Pulse Rate, and Temperature*

After signing informed consent, patients will be provided with a fingertip pulse oximetry device that connects to a mobile device connecting to a tablet that will be supplied to the patient to measure resting SpO₂ and resting pulse rate. Patients will be trained on the use of the device and tablet. This device will be used to determine study eligibility at Screening, and if the patient is eligible, he/she will return home with the device for remote monitoring of resting SpO₂ and resting pulse rate for the duration of the study.

6.2.1.1 *Screening*

Resting SpO₂ and resting pulse rate will be measured twice at Screening, with each measurement being of 2 minutes duration. For the first measurement, the patient will be sitting and breathing room air for at least 5 minutes before the measurement is made. A 3- to 5-minute interval will transpire before the second measurement is commenced. The patient should continue to sit and breath room air through the time that the second measurement is completed. To ensure stabilization of resting SpO₂, only the average of resting SpO₂ in the second minute of each measurement will be used to determine study eligibility. Resting pulse rate will also be determined during this time. To be eligible for the study, patients will be required to have an average resting SpO₂ $\geq 96.0\%$ on both measurements. Average resting pulse rate will also be determined from these measurements. Oral temperature will also be recorded.

6.2.1.2 *Home Monitoring*

Resting SpO₂ and resting pulse rate will be measured remotely twice daily at 09:00 hours and 16:00 hours for 14 days, with each measurement being of 2 minutes duration and with a 1-hour window around each time point. They will also record resting SpO₂ and resting pulse rate at any time they experience worsening symptoms. The patient will be sitting at rest and breathing room air for at least 5 minutes before these measurements are made and should continue to sit and breath room air through the time that the measurement is completed. To ensure stabilization of resting SpO₂ and resting pulse measurements, only the averages of these parameters in the second minute of measurement will be analyzed.

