9.9 Analysis of Efficacy Data

Efficacy analyses will be conducted using the mITT and PP Populations with the primary conclusions drawn from the mITT Population. Placebo will be the collective (pooled) across cohorts.

Descriptive statistics will be used to evaluate differences between Baseline and post-Baseline efficacy endpoints. The study is considered exploratory, and inferential statistics will be employed as appropriate.

For the purpose of study efficacy endpoints, resting SpO₂ and resting pulse rate will be assessed on observed data only; if data is missing, it will not be imputed.

The p-values from significance tests will be obtained at a one-sided significance level of 0.025.

No multiplicity adjustments will be made for the efficacy endpoints.

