9.9.2 Analysis of Continuous Data Endpoints

The continuous data endpoints – the secondary endpoints of average decrease in resting SpO₂ from Baseline and average increase in resting pulse rate from Baseline during the 14 days of home follow-up or hospitalization – will be tabulated by mean changes on each post-treatment day from baseline and their 95% CIs by NasoVAX cohort, pooled placebo, and overall NasoVAX groups. The p-values from parametric (ie, Pearson's t-test) or nonparametric (ie, Mann-Whitney test) tests will be calculated to see significant differences in continuous endpoints between each NasoVAX cohort and pooled placebo groups and between overall NasoVAX and pooled placebo groups.

Changes from Baseline in Severity of COVID-19, assessed by average decrease in resting SpO₂, average increase in resting pulse rate by outpatient pulse oximetry and COVID-19 symptoms (eDiary) during home follow-up, will also be analyzed using mixed model for repeated measures (MMRM). The MMRM model will include the fixed effects of treatment, days, and treatment-by-visit interaction, and the stratification factors (ages 35-64 years vs. ages 65 years and above, one or more risk factors present vs. no risk factors present). The model will also include the baseline characteristics (gender, race) and the corresponding baseline measures (resting SpO₂ at Baseline, resting pulse rate at Baseline). The model will employ an unstructured within patient covariance matrix and a restricted maximum likelihood estimation method.

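### SAP 9.9.2 fits a day-level MMRM with an unstructured covariance and names no small-sample method, target contrast or fallback, so its treatment-by-time test would be liberal

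*SAP*

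**What the plan says.** Protocol 10.3.2 describes the repeated-measures model for SpO2, pulse rate and symptoms this way: "The model will include the fixed effects of treatment, week, and treatment-by-visit interaction". SAP 9.9.2 changes the time factor: "The MMRM model will include the fixed effects of treatment, days, and treatment-by-visit interaction". It also adds the stratification factors, gender, race and the baseline measure. Both documents specify an unstructured matrix; the SAP's words are "The model will employ an unstructured within patient covariance matrix".

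Neither document defines what a visit is in the interaction term. Neither names a denominator degrees-of-freedom method, a contrast of interest, or a structure to use if the unstructured fit does not converge.

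SAP 9.9 sets the level for all efficacy tests: "The p-values from significance tests will be obtained at a one-sided significance level of 0.025". It makes no multiplicity adjustment and pools placebo across cohorts. Protocol 10.4 and SAP 9.13 let the SAP govern, so the day-level model is the one that would be run.

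**The concern.** Two weekly levels need 3 covariance parameters, and 14 daily levels need 105. An unstructured matrix of that size, estimated from fewer than 100 patients, is imprecise. A multi-degree-of-freedom Wald F test that treats it as well estimated rejects too often.

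The treatment-by-visit interaction is the only treatment-by-time term the SAP lists. Because no target contrast is named, nothing stops its p-value being reported as evidence of effect on SpO2, pulse rate or symptoms. If the fit does not converge, the analyst must choose another covariance structure with no pre-specified order, possibly after unblinding, and that choice can move the result.

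**Working it through.** The plan gives no power figure, covariance count or operating characteristic for this model, so there is no stated figure to reproduce.

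**Inputs**
- Time levels: 14 for days (SAP 9.9.2, home follow-up Days 1-14); 2 for weeks (Protocol 10.3.2).
- Alternative reading, with the single reading as the repeated unit: SpO2 and pulse rate are "measured remotely twice daily at 09:00 hours and 16:00 hours for 14 days", and "On Day 1, only the afternoon (16:00 hours) measurement is required" (SAP 4.2). That gives 1 + 13 × 2 = 27 readings.
- Patients: SAP 4.1 plans "approximately 10 and 14 patients in Cohorts 1 and 2, respectively, receiving NasoVAX and 10 and 14 receiving placebo" in Cohorts 1 and 2, and "Approximately 24 patients will receive NasoVAX and 24 will receive placebo in Cohort 3". The total is 48 v 48 = 96.
- With placebo pooled (SAP 9.9), Cohort 1 NasoVAX against placebo is 10 + 48 = 58, if that comparison is fitted on its own.
- Level: one-sided 0.025 for a directional test, taken as 0.05 for an F test.

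**Covariance parameters**, T(T + 1)/2:
- T = 2: 3
- T = 14: 14 × 15/2 = 105
- T = 27: 27 × 28/2 = 378

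**Exact size of the treatment-by-time test.** Assume complete data, two groups, no covariates, and the uncorrected Wald F statistic referred to F(q, ν), with q = T − 1 and ν = N − 2. By the Hotelling T² law, that statistic is distributed as ν/(ν − q + 1) times an F(q, ν − q + 1) variable. The true size is therefore P[F(q, ν − q + 1) > c × (ν − q + 1)/ν], where c is the 5% critical value of F(q, ν).

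| N | T | q | ν | ν − q + 1 | ν/(ν − q + 1) | c | True size |
|---|---|---|---|---|---|---|---|
| 96 | 2 | 1 | 94 | 94 | 1.000 | 3.942 | 5.0% |
| 96 | 14 | 13 | 94 | 82 | 1.146 | 1.826 | 10.4% |
| 96 | 27 | 26 | 94 | 69 | 1.362 | 1.614 | 28.3% |
| 58 | 2 | 1 | 56 | 56 | 1.000 | 4.013 | 5.0% |
| 58 | 14 | 13 | 56 | 44 | 1.273 | 1.899 | 15.9% |
| 58 | 27 | 26 | 56 | 31 | 1.806 | 1.694 | 56.3% |

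**Simulation with covariates.** Null data were analysed by unstructured REML with five time-constant covariates and between-patient degrees of freedom. The assumed correlation was 0.4 + 0.6 × 0.7^lag. Where data were missing, the assumption was 15% monotone dropout plus 5% intermittent loss. Sizes are at nominal 5%.

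| Comparison | Levels | Data | Runs | Interaction | Average over time | Last time point |
|---|---|---|---|---|---|---|
| 48 v 48 | 14 | complete | 1000 | 0.109 | 0.063 | 0.052 |
| 48 v 48 | 14 | missing | 600 | 0.127 | 0.077 | 0.070 |
| 10 v 48 | 14 | missing | 600 | 0.177 | 0.072 | 0.045 |
| 48 v 48 | 2 | missing | 1000 | 0.058 | 0.056 | 0.057 |
| 48 v 48 | 27 | missing | 200 | 0.530 | 0.040 | 0.050 |
| 10 v 48 | 27 | complete | 200 | 0.525 | 0.075 | 0.025 |

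The inflation is in the interaction column. The single-degree-of-freedom contrasts run from 0.025 to 0.077. The 27-level rows are approximate: 200 runs give a standard error near √(0.53 × 0.47/200) = 0.035.

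**Can the model be fitted?** With complete data, an unstructured fit needs the between-patient degrees of freedom to be at least T. With 58 patients there are 56, or about 51 after covariates. That exceeds 27, and all 200 simulated data sets gave an estimate.

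**The case against.** The strongest reply is that the plan's inference does not rest on the interaction test, and much of that stands. The endpoints in SAP 3.2 are an average decrease and an average increase, and the level is one-sided. An F test on 13 degrees of freedom has no direction, so a one-sided level points to a single-degree-of-freedom contrast, and those contrasts hold their size reasonably well. The MMRM is also an additional analysis beside the t-test or Mann-Whitney test (SAP 9.9.2) and the by-day ANCOVA (SAP 9.9.4), in a study described as exploratory. What does not stand is the inference that the target is therefore clear: the SAP never names it.

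Four stronger readings are tempting, and the documents do not support them.
- *That tests from this model are badly inflated in general.* Only the multi-degree-of-freedom treatment-by-time test is.
- *That the Cohort 1 model cannot be fitted.* That would hold for 27 readings in Cohort 1 alone (20 patients, 18 degrees of freedom). SAP 9.9 pools placebo, which gives 58 patients and an estimable model. A fit to Cohort 1 alone is also not the written model, because the age-group and risk-factor terms do not vary within that cohort. The general sentence on presentation across cohorts in SAP 9.1 does not override the specific efficacy rule.
- *That the model has 27 time points.* The SAP's named factor is days, its tabulation is by day, and the eDiary symptoms are daily. The 27-reading figures show what the ambiguity could cost; they do not describe the plan.
- *That the SAP improperly abandoned a clear protocol model.* The protocol already paired week with an undefined visit and an unstructured matrix, it does not define weekly means, and Protocol 10.4 allows the SAP to supersede on non-primary analyses.

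Nor does the calculation show that collapsing to weeks is necessary. With complete data, rescaling the statistic and referring it to F(q, ν − q + 1) restores 5% with 14 daily values.

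**Conclusion.** The point holds in a limited form. On the plain reading of SAP 9.9.2 (14 days), an uncorrected treatment-by-day test at nominal 5% has a true size of about 10% with all 96 patients and about 16% with 58. With covariates and assumed missing data, simulation puts these at about 13% and 18%. If single readings were the repeated unit, the complete-data figures would be about 28% and 56%. With two weekly levels the size is 5%.

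The exact figures assume complete data, no covariates, between-patient degrees of freedom and, for 58 patients, a separate fit for that comparison. The simulated figures also depend on the assumed correlation and missingness, since the documents give neither. Treatment contrasts on one degree of freedom stay near nominal, at most about 8%. Only secondary and symptom analyses are affected. It is a worthwhile, inexpensive clarification and does not threaten the primary analysis.

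**What to change.** In SAP 9.9.2:

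1. Define the repeated unit as the daily mean for SpO2 and pulse rate and the daily score for symptoms. Use the same term in the interaction (treatment-by-day), and record the change from the protocol's week.
2. Specify Kenward-Roger degrees of freedom.
3. Name the treatment difference averaged over Days 1-14 as the inferential contrast, and state that the interaction F test will not be used as evidence of effect.
4. List, in order, the covariance structures to try if the unstructured fit does not converge, and finalise that list before unblinding.

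Fitting two weekly means (Days 1-7 and 8-14) with a 2 × 2 unstructured matrix, in line with the protocol's week, is an acceptable alternative. It gives up day-level estimates from the model, although SAP 9.9.2 and 9.9.4 already provide daily summaries. Because home readings stop at hospitalization and only observed data are used, a weekly mean would also cover different days in different patients.

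The main option costs slightly wider intervals and a little more SAP text. It needs no new data and no change to study conduct.

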9.9.3 Analysis of Time to Event Data Endpoints

Time to event data endpoints – the primary endpoint of the first 4.0% decrease or greater from Baseline in resting SpO₂ on two consecutive measurements during the 14 days of home follow-

up, or hospitalization; the secondary endpoints of the first incidence of resting pulse rate ≥ 125 beats per minute during the 14 days of home follow-up, or hospitalization; and all-cause mortality through Day 42 – will be analyzed by the Kaplan-Meier method. The summary statistics will be tabulated by treatment arms over visits and will include number of patients without event, number patients censored, 25th, 50th, and 75th percentiles with 95% CIs, the event rates across all visits with 95% CIs. Kaplan-Meier estimates are calculated with the PROC LIFETEST procedure in SAS. The CIs of the event rates will be calculated via log-log transformation method (default option CONFTYPE=LOGLOG in SAS) based on standard errors computed using the Greenwood's formula. Time to event data comparisons will be made by treatment group and may include comparisons for cohort or stratification factors (ages 35-64 years vs. ages 65 years and above, one or more risk factors present vs. no risk factors present). The summary statistics may also have the p-values from log-rank test to compare changes in events between NasoVAX cohorts and pooled placebo and overall NasoVAX and pooled placebo groups. The log-rank test stratified by age groups and risk factors will also be performed. The Kaplan-Meier curves will also be plotted for each NasoVAX cohort and pooled placebo groups.

Non-informative censoring is assumed, as censored patients the same probability of experiencing an event as patients that remain in the study. Patients who do not meet the event or loss to follow-up before the study-end are censored at the last day during the 14 days of home follow-up or hospitalization in resting SpO₂ and resting pulse or at Day 42 for all-cause mortality.

9.9.4 *Analysis for Covariates*

Analysis of covariance (ANCOVA) will be used in the analysis of the secondary efficacy endpoints at each post-baseline visit, with the average decrease in resting SpO₂ from Baseline or the average increase in resting pulse rate from Baseline as a dependent variable, treatment arm as a factor, the stratification factors (ages 35-64 years vs. ages 65 years and above, one or more risk factors present vs. no risk factors present) and the corresponding baseline characteristics and measures (gender, race, resting SpO₂ at Baseline or resting pulse rate at Baseline) as covariates. This model will be generated using SAS PROC MIXED with treatment arm in the CLASS statement and visit/day in the BY statement. Comparisons of post-baseline average decrease in resting SpO₂ and average increase in resting pulse rate will be conducted for each NasoVAX dose group against the pooled placebo group. Least square (LS) means and 95% CIs of the LS means of treatment arm, difference of LS means and 95% CIs of the difference in LS means will be obtained from the model via ESTIMATE statements.

9.9.5 *Sensitivity and Post-Hoc Exploratory Analyses*

Sensitivity analyses may be performed to assess the effect of site on the response to study drug. Exploratory analyses of the efficacy data that are not identified in this SAP may also be conducted.

9.9.6 Handling of Missing Data

Efficacy analyses will be conducted based on observed data only. In sensitivity analyses, missing data due to death or hospitalization may also be imputed using the Last Observed Carried Forward (LOCF) or the multiple imputation methods. These analyses will be clearly identified as such in the Clinical Study Report.

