3.2 Secondary Efficacy Endpoints

Secondary efficacy endpoints are:

1. Maximal severity of COVID-19 after treatment, as assessed by the following:
 - average decrease in resting SpO₂ from Baseline resting SpO₂ at Screening during the 14 days of home follow-up or hospitalization
 - average increase in resting pulse rate from Baseline resting pulse rate at Screening during the 14 days of home follow-up or hospitalization
 - proportion of patients requiring hospitalization through Day 42 according to maximal level of oxygen supplementation:
 - No oxygen supplementation
 - Oxygen supplementation with nasal cannulae
 - Oxygen supplementation with high flow device or non-invasive ventilation
 - Mechanical ventilation
2. All-cause mortality through Day 42

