After discharge on Day 1, patients will return home for the duration of the study. Patients are to measure resting SpO₂, resting pulse rate, and oral temperature twice daily at 09:00 hours and 16:00 hours, with a 1-hour window around each time point, and at any time they experience worsening symptoms until Day 14 or hospitalization, whichever comes first. Patients are to record COVID-19-related symptoms daily during this same time period. Study center personnel will contact patients daily by telephone during this period to document the patient's clinical status, record concomitant medications and monitor for AEs.

After Day 14, study center personnel will contact patients via telephone approximately every 7±2 days for 14 additional days to determine if they were hospitalized and to follow AEs that were not resolved by Day 14. If the patient is hospitalized at any time, the dates and times of hospital admission/discharge, ICU admission/discharge, and ventilation requirement are to be recorded, as applicable. Patients who remain hospitalized at the end of 28 days will be followed through Day 42 or death, whichever is sooner.

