6.2.5 Additional Data Collection in Hospitalized Patients

Additional data to be collected for patients hospitalized due to COVID-19 through Day 42 to include the following:

- Date and time of hospital admission and discharge
- If transferred to ICU, date and time of ICU admission and discharge
- Requirement for oxygen (yes/no), and if yes, method of oxygenation (mask/nasal prongs, non-invasive ventilation, or high-flow oxygen; intubation and mechanical ventilation
 - If required ventilation, start date and time of ventilation, method of ventilation including whether intubated (yes/no)
- Change in ambulatory status
- Death

It is anticipated that most of this information will be obtained from the medical record. When necessary, a family member, designated legal representative or caregiver, as permitted by informed consent, will be contacted if the patient has expired or is too ill or otherwise unable to provide this information.

The rate (liters/min) of oxygen administered is to be captured as a concomitant medication. If, in the Investigator's opinion, a patient required a higher level of oxygenation, but did not receive due to resource availability, this should be documented.

Furthermore, if, in the Investigator's opinion, the patient required a higher level of care (ie, admittance to the ICU) but did not receive due to resource availability, this should be documented.

6.2.6 *Vital Status*

Vital status is to be documented at each study contact. If the patient died due to a reason other than COVID-19, the primary cause of death is to be recorded and reported as an SAE. Death due to worsening fever, cough, shortness of breath, resting SpO₂ or resting pulse rate or COVID-19 symptoms that are reported at Screening (Protocol Section 8.1.2) is not considered to be an SAE in the context of this study although cause of death will be reviewed by the DMC in real time.

6.3 **Safety Assessments**

6.3.1 *Height, Weight and Body Mass Index (BMI)*

Height (cm) and weight (kg) will be measured and recorded at Screening. BMI will be subsequently be calculated from these measurements.

6.3.2 *Physical Examination*

A cardiovascular and respiratory-focused physical examination will be performed by trained medical personnel during Screening.

6.3.3 *Screening Vital Signs*

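### The 14-day average SpO2 and pulse endpoints stop at hospitalization and use observed data only, so a difference between arms in hospitalization distorts them in a direction the trial cannot determine

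*SAP*

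**What the plan says.** SAP 3.2 places these averages under the heading "Maximal severity of COVID-19 after treatment, as assessed by the following". The pulse endpoint is the "average increase in resting pulse rate from Baseline resting pulse rate at Screening during the 14 days of home follow-up or hospitalization", and the SpO2 endpoint is worded the same way.

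Under SAP 4.1 (and Protocol 4.1), patients take home readings "until Day 14 or hospitalization, whichever comes first". SAP 6.2.1.2 sets the measuring condition: "The patient will be sitting at rest and breathing room air for at least 5 minutes before these measurements are made". For admitted patients, SAP 6.2.5 lists dates, ICU stay, ventilation, ambulatory status, death and "Requirement for oxygen (yes/no), and if yes, method of oxygenation". It lists no SpO2 or pulse series. The endpoint wording mentions hospitalization, but no section describes collecting these values in hospital.

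SAP 9.9 says SpO2 and pulse "will be assessed on observed data only; if data is missing, it will not be imputed". SAP 9.9.6 repeats the observed-data rule and adds that, in sensitivity analyses, "missing data due to death or hospitalization may also be imputed using the Last Observed Carried Forward (LOCF", with multiple imputation as the alternative. SAP 9.9.2 and 9.9.4 plan daily two-sample tests, an MMRM and a daily ANCOVA. No section says how admission or death enters the averages.

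**The concern.** Readings stop because the patient has become worse, so the outcome itself causes the missing data. An admitted patient's average covers only the days before admission, and the low values that would count most towards severity are never recorded. If one arm has more admissions, or earlier ones, it loses more of its worst days.

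What is at stake is the secondary objective on severity of disease, as measured by SpO2 and pulse. A reader of the study report would take the difference as covering 14 days, when it covers the days each patient was well enough to stay at home.

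**Working it through.** **Inputs.** The documents give 48 patients per arm, one-sided 0.025, a 14-day window and readings that end at admission. They give no expected hospitalization rate, SD or SpO2 course. The only rates are the stopping thresholds of 15%, 20% and 25% in SAP 5.1.2. There is no stated figure to reproduce, and everything below rests on assumptions.

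**Share of the window lost.** For admission on day d it is (14 − d + 1)/14:
- Day 3: 12/14 = 86%
- Day 7: 8/14 = 57%
- Day 11: 4/14 = 29%

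**Set-up 1 (assumed).** Admission is 15% on placebo and 5% on active. Patients not admitted do not fall. Admitted patients start to fall on Days 2–6, at 1.5 points/day to a floor of 8, and are admitted 2 or 3 days after onset. The difference is then (0.15 − 0.05) × m, where m is the mean fall per admitted patient.

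A hand check with onset on Day 4 takes the mean of admission on Day 6 and on Day 7:
- Full window, continued fall: (1.5 + 3 + 4.5 + 6 + 7.5 + 5 × 8)/14 = 4.46, so the difference is 0.45.
- Full window, flat after admission: the mean of 28.5/14 and 40.5/14 is 2.46, so 0.25.
- Observed average: the mean of 1.5/5 and 4.5/6 is 0.53, so 0.05.
- LOCF: the mean of 15/14 and 28.5/14 is 1.55, so 0.16.

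Simulation over all onset days gives:

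| Course after admission | Full 14 days | Observed | LOCF |
|---|---|---|---|
| Falls to floor 10 | 0.51 | 0.06 | 0.16 |
| Falls to floor 8 | 0.45 | 0.06 | 0.16 |
| Falls to floor 5 | 0.32 | 0.06 | 0.16 |
| Flat | 0.25 | 0.06 | 0.16 |
| Recovers 0.5/day | 0.13 | 0.06 | 0.15 |
| Recovers 1.0/day | 0.09 | 0.06 | 0.15 |
| Recovers 1.5/day | 0.07 | 0.06 | 0.16 |

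The last two columns use only readings before admission, so they cannot respond to what happens in hospital. The full difference changes about sevenfold (0.51/0.07) while they stay where they are.

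**Set-up 2 (different assumptions).** Admission is 15% and 7.5%, on Days 3–9. Admitted patients fall linearly to 4 points at admission, and the others fall 0.5. There are 60,000 simulated patients per arm. A sequential-regression likelihood estimate stands in for the MMRM. The last four columns give the share of the full difference that each analysis retains:

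| Course after admission | Full | Per-patient average | Daily means | LOCF | Likelihood |
|---|---|---|---|---|---|
| Worsens 1.5/day for 3 days | 0.37 | 30% | 12% | 45% | 30% |
| Worsens 0.5/day for 3 days | 0.27 | 43% | 17% | 64% | 42% |
| Flat | 0.21 | 53% | 21% | 82% | 52% |
| Prompt recovery | 0.08 | 144% | 58% | 214% | 141% |

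Three further cases, all with worsening of 1.5/day after admission:
- Equal rates and course: all differences are about 0, so there is no bias.
- Rates reversed (7.5% placebo, 15% active): the harm shrinks too, with 28% retained by the per-patient average and 44% by LOCF.
- Equal 15% rates, active only delays admission from Days 3–6 to Days 7–12: daily means retain −24% and the likelihood estimate −20%, so the sign reverses. The per-patient average retains 0% and LOCF 7%.

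**Missing at random.** After admission nobody is observed. The MMRM, or multiple imputation on the same assumption, fills those days from patients with similar earlier values who stayed at home. That is not the course of an admitted patient, which is why the likelihood column does no better than the per-patient average. Multiple imputation itself was not simulated, nor was pulse; the same reasoning applies to both.

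**The case against.** **The direction is not fixed.** A reader might infer that the difference is always biased toward zero and that every listed method errs the same way. The documents do not support this, because they record nothing of SpO2 after admission. LOCF overstates the difference once patients improve by 0.5 point/day (0.15 against 0.13). If the drug only delays admission, some estimates change sign.

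**LOCF is not the main cause.** A reader might also blame LOCF for the loss. It is optional, and when patients worsen or stay flat it comes nearer to the full difference than the observed data do. The observed-only rule in SAP 9.9 and 9.9.6 does most of the damage. What counts against LOCF is that its error changes direction with a course nobody will see.

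**The effect is not hidden from the trial.** It is tempting to say a benefit or harm would go unseen. Hospitalization is part of the primary endpoint (SAP 3.1). SAP 9.9.1 tests hospitalization proportions by Fisher and CMH tests, mortality is a separate endpoint, and hospitalization rates are a stopping rule. At an assumed 20% vs 5% with 48 per arm, Fisher's test on hospitalization has about 48% power. The rank test proposed here has about 24% (assuming a between-patient SD of 0.8, a reading SD of 1.0 and no effect in patients who stay home), and the observed averages 7%.

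**The full 14-day mean is hypothetical.** Admitted patients may be on oxygen, so a room-air mean over all 14 days could not be measured in everyone. A while-at-home average is a legitimate target. This stands, but the SAP does not say that it is the target, and the heading of maximal severity points the other way.

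**Conclusion.** The point holds for the two secondary averages only. They lose the course of the sickest patients after admission, and a difference between arms in the rate or timing of admission distorts the result. If patients worsen or stay flat in hospital, the distortion is attenuation: at an assumed 15% vs 5%, about 0.06 observed and 0.16 with LOCF, against 0.25 to about 0.51. If they recover at 0.5 to 1.5 points/day, the full difference is 0.07 to 0.13 and LOCF is too large. Missing-at-random methods do not resolve this. With equal rates and course there is no bias.

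The mechanism comes from the documents; the sizes come from assumed rates and trajectories. The study is exploratory and these endpoints carry no multiplicity adjustment, so this is a correction worth making, not a threat to the main result.

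**What to change.** In SAP 9.9.6, replace the optional LOCF with a sensitivity analysis that *will* be done: a van Elteren test on the 14-day average change, stratified by age group and risk factor, in which patients hospitalized by Day 14 rank below all others and deaths rank lowest. Keep the observed-data analysis and label it, in the SAP and in the tables, as a while-at-home average. Multiple imputation may remain as an option but does not fill this gap.

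No new data are needed: admission dates, deaths and strata are already recorded. The cost is SAP wording and one table. The downsides are a rank-based effect instead of SpO2 points, overlap with the hospitalization endpoint, and less power for a pure hospitalization effect than the test already planned.
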